### **9.2.1. Ramucirumab Dosing Schedule**

Ramucirumab will be dosed at 8 mg/kg and administered as a 1-hour IV infusion prior to the administration of LY2875358 on Days 1 and 15 of a 28-day cycle in Part A and B of this study. The infusion rate of ramucirumab should not exceed 25 mg/min.

#### **9.2.1.1. Premedication for Ramucirumab**

Premedication is recommended prior to infusion of ramucirumab. Recommended premedication agents include histamine H1 antagonists such as diphenhydramine hydrochloride 50 mg (or equivalent). Additional premedication may be provided at the investigator's discretion.

Premedication must be provided in the setting of a prior Grade 1-2 infusion-related reaction, as detailed in Section 9.2.3.1. All premedication administered must be adequately documented on the eCRF.

### **9.2.2. LY2875358 Dosing Schedule**

LY2875358 will be administered after a minimum of a 60-minute observation period (minimum of 30-minute observation period in Cycle 2 and beyond) following the end of the ramucirumab infusion on Days 1 and 15 of a 28-day cycle. LY2875358 will be administered as an IV infusion using either a central or a peripheral venous line. No in-line, sterile, nonpyrogenic filter should be used. To ensure that the total dose of LY2875358 will be administered, the line should be flushed at the end of the infusion (see pharmacy instructions). The LY2875358 infusion, including the flushing of the line, should be administered over a period of approximately 90 minutes. If it is determined that a reduced LY2875358 infusion time is safe and feasible, the investigators will be notified in writing and the pharmacy instructions will be updated to reflect the change.

No premedication is recommended prior to infusion of LY2875358. Premedication may be provided at the investigator's discretion. Premedication must be provided in the setting of a prior Grade 1-2 infusion-related reaction, as detailed in Section 9.2.3.1. All premedication administered must be adequately documented on the eCRF.

#### **9.2.2.1. Dose Escalation of LY2875358 in Part A**

In Part A, dose levels of LY2875358 previously tolerated as monotherapy and in combination with erlotinib in Study JTBA will be administered following the proposed dose escalation scheme below:

**Dose level 1:** LY2875358 750-mg flat dose as a 90-minute IV infusion after a minimum of a 60-minute observation period (minimum of 30-minute observation period in Cycle 2 and beyond) following the end of the ramucirumab 8-mg/kg infusion on Days 1 and 15 of a 28-day cycle

**Dose level 2:** LY2875358 2000-mg flat dose as a 90-minute IV infusion after a minimum of a 60-minute observation period (minimum of 30-minute observation period in Cycle 2 and beyond) following the end of the ramucirumab 8-mg/kg infusion on Days 1 and 15 of a 28-day cycle

Dose escalation will be guided primarily by safety assessments, in particular AEs, during Cycle 1. By nature of being a dose escalation study, data will be evaluated on an ongoing basis to determine a recommended schedule and dose range of LY2875358 that may be safely administered in combination with ramucirumab on Days 1 and 15 of a 28-day cycle.

The sponsor and investigators will review and discuss all patient safety data prior to dose escalation. In addition, if available at the time of dose escalation decision, PK results will be used as secondary/supporting data for dose escalation. Intermediate dose levels for LY2875358 (or a dose below the starting dose) may be considered based on appearance of toxicity or PK/PD modeling, if deemed appropriate by agreement between the investigators and the sponsor. If during the dose escalation, a new sequence of drug administration (eg, inverse order of administration or sequential dosing of the study drugs on separate days) should be indicated for safety or PK reasons, or preclinical data suggest that this may pose a better regimen, then the investigators together with the sponsor will decide on this change and inform the ERBs in writing. No protocol amendment will be required.

No dose escalation can occur without prior discussion and agreement between the investigator and the Lilly CRP/CRS; the decision will be documented in writing. Based on the ongoing safety reviews, modifications to the dose escalation strategy or other design elements may be made via protocol amendment to ensure patient safety. Intrapatient dose escalation will not be permitted in this study.

For assessment of toxicity the standard scoring system, Common Terminology Criteria for Adverse Events (CTCAE) Version 4.0, established by the National Cancer Institute (NCI) (NCI 2010) will be used. A minor version of CTCAE Version 4.0 (eg, CTCAE Version 4.03) may be used for this study. Minor updates to CTCAE Version 4.0 will not necessitate a protocol amendment, and the use of an updated CTCAE Version 4.0 will not be considered a protocol violation. Any AEs related to study drugs will be considered as toxicities.

### **9.2.2.2. Dose-Limiting Toxicity Determination**

Dose-limiting toxicity is defined as an AE during Cycle 1 that is possibly, probably, or definitely related to treatment with LY2875358 in combination with a fixed regimen of ramucirumab and fulfills any 1 of the following criterion using the NCI CTCAE Version 4.03:

- $\geq$ Grade 3 non-hematological toxicity. Exceptions will be made for:
  - nausea, vomiting, diarrhea, constipation, or skin rash that persists for  $\leq$ 3 days following appropriate supportive care intervention
  - Grade 3 hypertension in which systolic BP  $\geq$ 160 mmHg and/or diastolic BP  $\geq$ 100 mmHg persist  $<$ 7 days after intensified antihypertensive therapy is initiated
- Grade 4 hematological toxicity of  $\geq$ 7 days duration
- $\geq$ Grade 3 thrombocytopenia with  $\geq$ Grade 2 bleeding
- Any febrile neutropenia

- Any other significant toxicity deemed by the primary investigator and Lilly clinical research personnel to be dose-limiting (eg, any toxicity that is possibly related to the study medication that requires the withdrawal of the patient from the study during Cycle 1).

Infusion-related reactions (including hypersensitivity reactions and anaphylaxis) should not be considered as DLTs unless the investigator or Lilly medical monitor provides compelling rationale to support their inclusion as a DLT.

Patients in Part A (Cycle 2 or greater) and Part B will be evaluated on an ongoing basis for AEs. In these patients, a DLT-equivalent toxicity will be defined based on trends of any clinical significant toxicity deemed by the study investigators and Lilly clinical research personnel to be dose-limiting and related to study drug(s). The investigators and Lilly CRP/CRS will have to agree as to whether such AEs are considered as DLT-equivalent.

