#### **9.2.2.3. Dose Escalation Method and Maximum Tolerated Dose Definition**

In this study, a 3+3 dose-escalation paradigm will be utilized. If 1 patient, at any dose level, experiences a DLT during the DLT period (Cycle 1), then up to 3 additional patients will be enrolled at that dose level. If a DLT is observed in  $\geq 2$  out of 6 patients at any dose level, dose escalation will cease and either the previous dose level will be declared the maximum tolerated dose (MTD) or, following discussions between the investigators and the sponsor, additional patients may be treated at intermediate doses between the previous and the current dose levels.

The first patient enrolled in Part A in this study will be observed for a DLT (as defined in Section 9.2.2.2) during the first 14 days of Cycle 1, before subsequent patients are treated at that dose level. If the first patient does not experience a DLT during this period, subsequent patients may be concurrently enrolled at the initial cohort. In subsequent cohorts, all patients may be enrolled concurrently.

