### **9.2.3. Dose Adjustments and Delays**

In Cycle 1, no dose adjustments, or delays of ramucirumab and/or LY2875358 will be allowed (ie, DLT assessment period), except in case of any DLT.

In Cycle 2 or beyond, if a patient experiences a toxicity warranting a dosing delay in the investigator's opinion, ramucirumab and/or LY2875358 dosing may be held for up to 2 consecutive doses (approximately 28 days) to allow sufficient time for recovery from the toxicity. This approximate 28-day time period begins on the day that the next dose of study treatment should have been administered but was withheld for toxicity. If both study drugs were held due to a toxicity, study treatment with both study drugs should be resumed as soon as that toxicity is resolved, provided that the patient did not meet any discontinuation criteria.

In case the toxicity is specifically attributable to 1 of the 2 experimental study drugs in the opinion of the investigator (eg, ramucirumab-related hypertension), the patient may continue to receive the other study drug following the regularly scheduled Q2W treatment time points (eg, LY2875358). In this setting, treatment of the withheld study drug (eg, ramucirumab) should be resumed at the next regularly scheduled Q2W treatment time point of the continued study drug (eg, LY2875358) following the resolution of the event causing the hold. Make-up doses of the withheld study drug occurring between regularly scheduled Q2W treatment time points are not permitted in order to keep the administration of both study drugs synchronized to the same study days (ie, Day 1 or 15 of a cycle). In situations where >2 consecutive doses have been missed, events related to the missed doses have resolved, and there is evidence of ongoing disease control, continuation of ramucirumab and/or LY2875358 may be considered and must be discussed with the Lilly clinical team.

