### **9.2.3.2. Treatment Guidelines and Dose Modifications for Ramucirumab-specific Adverse Events**

Dose modifications of ramucirumab are permitted in the setting of non-life-threatening, reversible Grade 3-4 clinical AEs (eg, fever) considered to be at least possibly related to ramucirumab.

- For toxicities that resolve to Grade  $\leq 1$  or baseline, ramucirumab may be re-administered at a dose of 8 mg/kg
- If a second instance of such an event occurs, ramucirumab should be subsequently re-administered at a dose of 6 mg/kg Q2W.
- A second dose reduction to 5 mg/kg Q2W is permitted for this level of event (Grade 3-4).

Any further dose reduction of ramucirumab below 5 mg/kg is not permitted, and if the criteria for a ramucirumab dose reduction are met for patients at 5 mg/kg ramucirumab Q2W, ramucirumab must be discontinued. If the dose of ramucirumab is reduced, subsequent dose increases are not permitted. If a patient's dose is reduced or treatment is discontinued as a result of an AE, study site personnel must clearly report the circumstances and data leading to any such dosage reduction or discontinuation of treatment.

Patients who enter the study with symptoms or laboratory values equivalent to NCI-CTCAE Version 4.03 Grade 1-2 AEs should not have dose reductions related to the persistence or mild worsening of those symptoms or laboratory values; dose reductions may be warranted if worsening of symptoms or laboratory values is clinically significant in the opinion of the investigator. Asymptomatic Grade 3-4 laboratory abnormalities should not result in dose interruptions, modifications, or discontinuation of study therapy unless determined to be clinically significant by the investigator (or unless otherwise specified in the study protocol).

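### The DLT exemption for brief nausea, vomiting, diarrhea, constipation or rash names no grade, so a short Grade 4 event is a DLT only by judgment while a 4-day Grade 3 event is one by rule

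*Protocol*

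**What the plan says.** Protocol 9.2.2.2 defines a DLT as a Cycle 1 adverse event at least possibly related to the combination that meets any one of several criteria. The first is non-hematological toxicity of Grade 3 or higher, with two exemptions:

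- "nausea, vomiting, diarrhea, constipation, or skin rash that persists for" at most 3 days after appropriate supportive care. No grade is named.
- "Grade 3 hypertension in which systolic BP" or diastolic pressure stays above set limits for less than 7 days on intensified treatment. This one is limited to Grade 3.

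Two other criteria matter here. The hematological one begins "Grade 4 hematological toxicity of" and requires at least 7 days, so shorter Grade 4 hematological events are excused. The catch-all covers "Any other significant toxicity deemed by the primary investigator and Lilly clinical research personnel to be dose-limiting". SAP 6.11 carries the same definition.

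DLT status is used in three places:

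- Protocol 9.2.2.3: if one patient has a DLT, "then up to 3 additional patients will be enrolled at that dose level", and escalation stops at 2 or more of 6.
- Protocol 9.2.2.3: the first Part A patient "will be observed for a DLT (as defined in Section 9.2.2.2) during the first 14 days of Cycle 1" before others are treated at that level.
- Protocol 9.2.3: in Cycle 1, "no dose adjustments, or delays of ramucirumab and/or LY2875358 will be allowed (ie, DLT assessment period), except in case of any DLT".

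**The concern.** The criterion being relaxed reaches above Grade 3, so an exemption limited only by duration reaches above Grade 3 too. Neither document adds a ceiling elsewhere. The result is an inversion: the more severe event can fall outside the rule while a less severe but slightly longer one falls inside it.

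Unless it is deemed dose-limiting, a brief Grade 4 event does not count toward expansion or stopping, does not hold the first-patient gate, and does not open the Cycle 1 delay allowance. That last consequence is narrow. An exempt event bears on the Day 15 dose only if it starts shortly before it, and Protocol 9.2.3.2 may separately allow a ramucirumab hold: "Dose modifications of ramucirumab are permitted in the setting of non-life-threatening, reversible Grade 3-4 clinical AEs" considered at least possibly related to it. The corresponding hold rule for LY2875358 (Protocol 9.2.3.3) begins only in Cycle 2.

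What is at stake is whether the 3+3 count rests on a written rule or on a case-by-case decision for these five terms.

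**Working it through.** The plan states no figure that depends on this wording, so there is nothing of its own to reproduce. The check has a textual part and an illustrative calculation.

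**Applying the text.** Both cases are related and occur in Cycle 1; duration is counted from supportive care, as the protocol counts it.

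| Event | First criterion | Exemption met? | DLT status |
|---|---|---|---|
| Grade 4 diarrhea, settles within 3 days | Grade 3 or higher: yes | Yes | Only if deemed so under the catch-all |
| Grade 3 diarrhea, lasts 4 days | Grade 3 or higher: yes | No | Automatic |

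The protocol does not say whether persistence means at Grade 3 or above or at any grade. That does not affect the missing ceiling.

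**Inputs for size.**

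- The documents give no rate for brief Cycle 1 Grade 4 events in these terms. The nearest figure is in Protocol 5.2.2: one possibly related nausea event of Grade 3 or higher, against 123 monotherapy patients. 1/123 = 0.81%. Its exact grade, cycle and duration are not given.
- f, the share of that class that is brief, Cycle 1 and Grade 4: assumed 10% to 50%. Then q = f/123 = 0.08% to 0.41%.
- d, the rate of other DLTs per patient: assumed 5%, 10% and 20%.

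**Formulas.** A level clears with 0 of 3 DLTs, or with 1 of 3 followed by 0 of 3:

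P(clear) = (1−p)³ + 3p(1−p)² × (1−p)³.

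With brief Grade 4 events exempt, p = d. With them counted, p = 1 − (1−d)(1−q).

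For d = 0.10, exempt: 0.729 + 0.243 × 0.729 = 0.9061.
For f = 0.50, counted: p = 1 − 0.90 × 0.99593 = 0.1037, and P(clear) = 0.9001.

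| d | Exempt | Gap, f = 10% | Gap, f = 25% | Gap, f = 50% | Gap, f = 100% |
|---|---|---|---|---|---|
| 5% | 97.3% | 0.08 | 0.20 | 0.40 | 0.82 |
| 10% | 90.6% | 0.12 | 0.30 | 0.61 | 1.23 |
| 20% | 70.9% | 0.14 | 0.35 | 0.70 | 1.41 |

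Gaps are in percentage points. The last column treats the whole 0.81% class as brief Cycle 1 Grade 4 events, which probably overstates the effect unless the combination raises the rate.

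**Chance that the question arises at all.** P(at least one) = 1 − (1−q)ⁿ. For f = 10%: 0.49% with 6 patients and 0.97% with 12. For f = 50%: 2.41% and 4.77%. So roughly 0.5% to 4.8% over Part A.

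**If it does arise.** Suppose exactly one such event in the first 3 patients, none in the next 3, and the catch-all not used. Exempt, the level clears with probability 90.6% (d = 10%). Counted, the other two patients and all three added ones must be free of other DLTs: (1−d)⁵ = 0.90⁵ = 59.0%. For d = 5% and 20% the counted figures are 77.4% and 32.8%.

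**The case against.** The strongest reply is that a duration-based approach is consistent with the rest of the definition and may be deliberate. Grade 4 hematological toxicity under 7 days is excused, and infusion-related reactions, including anaphylaxis, are kept out of DLT status by default with no grade limit, although Table JTBF.3 includes life-threatening Grade 4 forms. Judgment is the backstop in each case. This stands as a reason not to call the wording an error. It does not remove the ambiguity: the hypertension exemption and the hematological criterion state their grades, and this exemption neither does so nor explains why.

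A reader might infer that a dangerous event could go unnoticed, or that the patient would have to be re-dosed on Day 15. The documents support neither. All safety data are reviewed, and escalation needs written agreement (Protocol 9.2.2.1). Unacceptable related toxicity leads to discontinuation of study drug, and the investigator may withdraw a patient, with no restriction to later cycles (Protocol 8.2.1). Life-threatening events are SAEs, reportable within 24 hours (Protocol 10.1.2.1). The 3+3 rule does not compel escalation. These safeguards hold, and they reduce the point to how the event is classified and counted.

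It is also fair that the size rests on one nausea event of unstated exact grade and an assumed share, and that the documents do not reproduce the CTCAE grading for these five terms.

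**Conclusion.** The point holds as a minor one. The exemption has no grade ceiling, so a brief related Grade 4 event in these terms is a DLT only by decision of the investigator and sponsor, while a 4-day Grade 3 event is one by rule. It would be too strong to say that such an event cannot be a DLT; the catch-all is not barred.

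The expected effect is small: about 0.1 to 0.6 points on the chance of clearing a level with other DLTs at 10%, and 0.1 to 0.7 points across 5% to 20%. This rests on 1/123 as a proxy, an assumed 10% to 50% share, and monotherapy experience carrying over to the combination.

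A reader might take 59.0% against 90.6% as the size of the problem. It is not. That contrast applies only if such an event occurs among the first 3 patients and the catch-all is not used; under the same assumptions, any such event across 6 to 12 Part A patients has a 0.5% to 4.8% chance.

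**What to change.** For any Part A dose-escalation patients still to be assessed, insert Grade 3 at the start of the exemption in Protocol 9.2.2.2 and SAP 6.11, matching the hypertension item. Any related Cycle 1 event of Grade 4 or higher in these terms then counts automatically. The cost is one inserted term in each document; grades are already collected. The downside is that a dose level may be expanded or stopped slightly more often, by the 0.1 to 0.6 points above.

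Part A may already be over. SAP 5.1 says the protocol was amended before Part B began and that the NSCLC cohort was added in light of Part A safety, though neither document states completion outright. If it is complete, keep the prespecified definition rather than reclassifying events afterwards. The planned summary of TEAEs by maximum grade (SAP 6.11.2) and the SAE listing (SAP 6.11.3) largely cover disclosure, so a separate listing of exempted events would add little.

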#### **9.2.2.3. Dose Escalation Method and Maximum Tolerated Dose Definition**

In this study, a 3+3 dose-escalation paradigm will be utilized. If 1 patient, at any dose level, experiences a DLT during the DLT period (Cycle 1), then up to 3 additional patients will be enrolled at that dose level. If a DLT is observed in  $\geq 2$  out of 6 patients at any dose level, dose escalation will cease and either the previous dose level will be declared the maximum tolerated dose (MTD) or, following discussions between the investigators and the sponsor, additional patients may be treated at intermediate doses between the previous and the current dose levels.

The first patient enrolled in Part A in this study will be observed for a DLT (as defined in Section 9.2.2.2) during the first 14 days of Cycle 1, before subsequent patients are treated at that dose level. If the first patient does not experience a DLT during this period, subsequent patients may be concurrently enrolled at the initial cohort. In subsequent cohorts, all patients may be enrolled concurrently.

#### **9.2.2.4. Dose Confirmation of LY2875358 in Part B**

Once a recommended schedule and dose range of LY2875358 that may be safely administered in combination with ramucirumab on Days 1 and 15 of a 28-day cycle has been determined in Part A, the tumor expansion portion of the study (Part B) will be opened. Approximately 15 patients in each of the 4 specified tumor types will be enrolled (approximately 60 patients in total). The dose and schedule of LY2875358 in Part B for combination with the fixed regimen of ramucirumab 8 mg/kg Q2W will be defined based upon safety, PK/PD, and antitumor activity observed in Part A. The sponsor, in collaboration with the investigators, will review Part A results prior to determining the recommended schedule and dose of LY2875358 to be studied in Part B. The decision will be documented in writing and a written notification will be sent to the IRB prior to enrollment of patients into Part B. No amendment will be required. If indicated by safety, PK/PD, and/or emerging clinical data, the recommended schedule and dose of LY2875358 and ramucirumab in Part B might be individually adjusted for each tumor cohort following written notification by the sponsor.

### **9.2.3. Dose Adjustments and Delays**

In Cycle 1, no dose adjustments, or delays of ramucirumab and/or LY2875358 will be allowed (ie, DLT assessment period), except in case of any DLT.

In Cycle 2 or beyond, if a patient experiences a toxicity warranting a dosing delay in the investigator's opinion, ramucirumab and/or LY2875358 dosing may be held for up to 2 consecutive doses (approximately 28 days) to allow sufficient time for recovery from the toxicity. This approximate 28-day time period begins on the day that the next dose of study treatment should have been administered but was withheld for toxicity. If both study drugs were held due to a toxicity, study treatment with both study drugs should be resumed as soon as that toxicity is resolved, provided that the patient did not meet any discontinuation criteria.

In case the toxicity is specifically attributable to 1 of the 2 experimental study drugs in the opinion of the investigator (eg, ramucirumab-related hypertension), the patient may continue to receive the other study drug following the regularly scheduled Q2W treatment time points (eg, LY2875358). In this setting, treatment of the withheld study drug (eg, ramucirumab) should be resumed at the next regularly scheduled Q2W treatment time point of the continued study drug (eg, LY2875358) following the resolution of the event causing the hold. Make-up doses of the withheld study drug occurring between regularly scheduled Q2W treatment time points are not permitted in order to keep the administration of both study drugs synchronized to the same study days (ie, Day 1 or 15 of a cycle). In situations where >2 consecutive doses have been missed, events related to the missed doses have resolved, and there is evidence of ongoing disease control, continuation of ramucirumab and/or LY2875358 may be considered and must be discussed with the Lilly clinical team.

It is recognized that, in the course of clinical cancer care, it is not always possible to schedule therapeutic infusions precisely 2 weeks following a prior infusion (ie, because of holidays, travel difficulties, or other circumstances). Accordingly, study drug infusions administered within the timing window as indicated in the Study Schedule (see [Attachment 1](#)) relative to the regularly scheduled Q2W treatment time point will be considered acceptable. Moreover, in Cycle 3 or beyond, ramucirumab and LY2875358 dosing may be delayed for up to approximately 14 days because of holidays, weekends, inclement weather, or other justifiable events, and not counted as a protocol violation. This approximate up to 14-day time period begins on the day that the next dose of study treatment should have been administered. In order to keep the administration of both study drugs synchronized, the next dose of ramucirumab and LY2875358 should be administered at the same study day to continue the regularly scheduled Q2W treatment time points.

In the event of dosing delays or missed doses, disease assessment and imaging studies should be undertaken according to the original study schedule, regardless of the actual number of on-study treatments received.

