#### **9.2.3.2.1. Hypertension**

The following are treatment guidelines for hypertension that develops during the study.

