##### Grade $\leq 3$

- If the hypertension is not associated with symptoms, continue ramucirumab and initiate antihypertensive therapy.
- If the hypertension is associated with symptoms, hold ramucirumab until symptoms resolve and initiate antihypertensive therapy.
- If ramucirumab is held more than once for hypertension (ie, symptomatic hypertension, markedly elevated BP unresponsive to antihypertensive therapy), the dose of investigational product should be reduced upon re-treatment to 6 mg/kg Q2W. A second

dose reduction to 5 mg/kg Q2W should be undertaken if an additional postponement of ramucirumab is required.

Grade 3 (systolic BP  $\geq 160$  mmHg or diastolic BP  $\geq 100$  mmHg; medical intervention indicated; more than 1 drug or more intensive therapy than previously used indicated)

- For Grade 3 hypertension not associated with symptoms, continue ramucirumab with more intensive antihypertensive therapy. If systolic BP remains  $\geq 160$  mmHg or diastolic BP remains  $\geq 100$  mmHg  $>3$  weeks after initiation of additional antihypertensive therapy, hold ramucirumab while continuing appropriate antihypertensive therapy.
- If the hypertension is associated with symptoms, hold ramucirumab while continuing appropriate antihypertensive therapy.
- If ramucirumab is held more than once for hypertension (ie, symptomatic hypertension, markedly elevated BP unresponsive to antihypertensive therapy), the dose of ramucirumab should be reduced upon re-treatment to 6 mg/kg Q2W. A second dose reduction to 5 mg/kg Q2W should be undertaken if an additional postponement of investigational product is required.

Grade 4 or refractory

- Patients with Grade 4 hypertension (life-threatening consequences, eg, malignant hypertension, transient or permanent neurologic deficit, hypertensive crisis, or urgent intervention indicated) or patients whose hypertension is poorly controlled ( $>160$  mmHg systolic BP or  $>100$  mmHg diastolic BP for  $>4$  weeks) despite appropriate oral medication ( $>2$  oral agents at MTD) will be discontinued from ramucirumab.

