#### **9.2.3.2.2. Proteinuria**

If, while receiving ramucirumab, a patient has proteinuria  $\geq 2+$  per a dipstick or routine urinalysis test, ramucirumab will continue as scheduled, and a 24-hour urine collection will be conducted prior to the subsequent scheduled treatment cycle. If the protein level is  $<2$  g/24 hours, the patient will continue on ramucirumab at the same dose without interruption. If the protein level is 2 to 3 g/24 hours, ramucirumab for the subsequent cycle will be held for 2 weeks and a 24-hour urine collection will be repeated. Treatment with ramucirumab will resume at a reduced dose level (6 mg/kg Q2W) once the protein level returns to  $<2$  g/24 hours. A second dose reduction of ramucirumab to 5 mg/kg every 2 weeks is permitted if proteinuria  $>2$  g/24 hours recurs. Ramucirumab will be discontinued if the protein level is  $>3$  g/24 hours, if there is a third occurrence of proteinuria  $>2$  g/24 hours, or if the protein level does not return to  $<2$  g/24 hours within 2 weeks.

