#### **9.2.3.2.3. Thromboembolic Events**

Investigators should perform all testing required to fully characterize arterial or venous thromboembolic/vascular events. The incidence and type of thromboembolic/vascular events will be collected and reported. Ramucirumab should be discontinued in the event of any Grade 3-4 ATE or VTE that is considered by the investigator to be life-threatening, or symptomatic and not adequately treated by anticoagulation therapy. Ramucirumab may be continued in the setting

of an incidentally diagnosed, asymptomatic deep vein thrombosis or pulmonary embolism, or following these events when symptoms have resolved with the institution of anticoagulation therapy. Ramucirumab should also be discontinued in the setting of a deep vein thrombosis or pulmonary embolism that occurs or intensifies while the patient is receiving therapeutic anticoagulation therapy.

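### For symptomatic hypertension below Grade 3 at Cycle 1 Day 15, Protocol Section 9.2.3 forbids holding ramucirumab, Section 9.2.3.2.1 directs a hold, and neither is said to prevail

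*Protocol*

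**What the plan says.** Protocol Section 9.2.3 opens with the Cycle 1 rule: "no dose adjustments, or delays of ramucirumab and/or LY2875358 will be allowed (ie, DLT assessment period), except in case of any DLT". Its permission to delay for other toxicity, on the investigator's judgment, begins with Cycle 2.

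Section 9.2.3.2.1 has a wider scope: "The following are treatment guidelines for hypertension that develops during the study". Under its heading for Grade 3 or lower it directs: "If the hypertension is associated with symptoms, hold ramucirumab until symptoms resolve and initiate antihypertensive therapy". Under its separate Grade 3 heading it directs: "If the hypertension is associated with symptoms, hold ramucirumab while continuing appropriate antihypertensive therapy". Neither instruction mentions a cycle.

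Section 9.2.2.2, repeated in SAP Section 6.11, starts non-hematological DLTs at Grade 3. It exempts Grade 3 hypertension when the raised pressure lasts fewer than 7 "days after intensified antihypertensive therapy is initiated". It also has a discretionary item: "Any other significant toxicity deemed by the primary investigator and Lilly clinical research personnel to be dose-limiting".

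Other hold rules avoid the Cycle 1 ban by their own wording. The LY2875358 hold in Section 9.2.3.3 starts at Cycle 2. For proteinuria, Section 9.2.3.2.2 says that "ramucirumab for the subsequent cycle will be held for 2 weeks".

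**The concern.** This is a safety dosing instruction with two incompatible answers. A site that holds the Day 15 dose departs from the letter of Section 9.2.3. A site that gives it departs from the hypertension guidance and infuses an anti-VEGFR-2 antibody into a patient with symptomatic hypertension. Section 9.2.3.2.9 calls hypertension an identified risk of ramucirumab and relies on Section 9.2.3.2.1 to control blood pressure, so the hold is not incidental advice.

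The same event could be handled differently from site to site. It would also be unclear whether a patient whose dose was held had deviated from the protocol, and how that patient counts in the DLT assessment.

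**Working it through.** No statistical figure is involved. The check sets the rules side by side and follows one case through them.

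1. **Is a hold a delay?** Yes, in the protocol's own usage. In its Cycle 2 paragraph, Section 9.2.3 describes a toxicity that warrants a delay and then says that dosing may be held. The Cycle 1 ban on delays therefore covers a hold.

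2. **Is the event a DLT?** Below Grade 3, not by the listed grade criteria. Section 9.2.3.2.1 describes Grade 3 by pressure (systolic at least 160 or diastolic at least 100 mmHg) and also by the need for more than one drug or for more intensive therapy than before. The clear case must be below Grade 3 on both counts. The heading for Grade 3 or lower pairs the hold with starting antihypertensive therapy, so I read starting treatment as not enough by itself to make the event Grade 3.

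3. **When does it bite?** Ramucirumab is given on Days 1 and 15 of a 28-day cycle (Section 9.2.1), so one Cycle 1 dose follows first exposure. Attachment 1 allows Day 15 ±1 day, and the last in-window day is 15 + 1 = Day 16. If symptoms resolve by then, there is no conflict.

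4. **The case.** Take symptomatic Grade 2 hypertension, present on Day 15, persisting past Day 16, and not declared dose-limiting. Section 9.2.3 does not allow the hold and Section 9.2.3.2.1 directs it. Both cannot be followed.

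5. **Is it isolated?** Of the nine subsections 9.2.3.2.1 to 9.2.3.2.9, two expressly order a temporary hold (hypertension and proteinuria), and only hypertension has no cycle limit. Section 9.2.3.2.3 implies a hold for symptomatic thrombosis, since it lets ramucirumab continue "following these events when symptoms have resolved with the institution of anticoagulation therapy", but it does not order one. Outside that count, the infusion-reaction rules in Section 9.2.3.1 also have no cycle limit. They slow, interrupt or permanently stop a drug, although Section 9.2.2.2 says such reactions are ordinarily not DLTs.

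6. **Is there a precedence rule?** None was found in either document. The authors did write one elsewhere: Section 9.2.3.2 yields to other protocol text for asymptomatic laboratory abnormalities.

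7. **Dose consequence if the hold is followed.** 1 of the 2 planned Cycle 1 ramucirumab doses is at stake. Where LY2875358 continues, Section 9.2.3 bars make-up doses, so the next ramucirumab dose falls on Cycle 2 Day 1, which is Day 28 + 1 = 29. The interval is 29 - 1 = 28 days instead of 15 - 1 = 14. The make-up paragraph states no cycle but follows the Cycle 2 paragraph, so applying it in Cycle 1 is a reading.

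8. **Evaluability.** Section 9.6.1 makes Cycle 1 noncompliance non-evaluable only when the reason is not drug-related toxicity. It also seeks at least 3 patients who complete one cycle at each dose level. SAP Section 6.11.1 counts a cycle as completed only if all planned treatment was received. A patient held for toxicity without a DLT is neither discontinued nor noncompliant, yet is not a completer. The plan does not say how that patient counts.

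**The case against.** The strongest reply is that no sensible site would be misled. Section 9.2.3.2.1 is introduced as guidelines, and a specific safety rule is normally read over a general one. Section 9.2.3.1 supports this: nobody would dose on Day 15 after a Grade 4 infusion reaction merely because such reactions are not ordinarily DLTs. The event-specific rules must therefore operate in Cycle 1. The investigator is responsible for medical care and may stop treatment (Sections 10.1.1 and 8.2.1). The discretionary DLT item could also bring an event within the exception in Section 9.2.3.

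Much of this stands as evidence of what was meant, and "directs" is a fairer verb than "requires". None of it is written as the resolution, and the Cycle 1 ban is itself specific, with a single stated exception. The discretionary item needs agreement between the investigator and the sponsor's personnel. It would also put a low-grade event into the 3+3 count, where one DLT triggers up to 3 more patients and at least 2 of 6 stops escalation (Section 9.2.2.3).

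A second reply is timing. SAP version 2, approved in November 2014, says that Part B4 was added in light of Part A safety, and this protocol version was approved in March 2015. Part A results appear to have been in use already, so a correction now might reach few Part A patients. That is an inference from the dates, but a fair one, and it limits the practical gain.

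**Conclusion.** The contradiction is real and should be corrected, as an internal inconsistency between two stated safety rules. Its clear extent is symptomatic hypertension that is below Grade 3 by pressure and by treatment need, persists past Cycle 1 Day 16, and is not declared dose-limiting. The population is mainly Part A, about 6-12 patients (Section 8.1.1) with one exposed dosing day each. The documents give no rate for this event. The 16% hypertension in the gastric Phase 3 trial (Section 5.2.1.1) counts all hypertension and cannot stand in for it. The frequency is probably low.

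A reader might infer three stronger points that the documents do not support:

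- **That the dose decision is biased.** This is not shown. Section 9.2.2.1 has the sponsor and investigators review all patient safety data before escalation.
- **That Grade 3 is equally caught.** This is only arguable. A related Grade 3 event still in progress can be read as a DLT until the under-7-day exemption is met.
- **That Part B is equally caught.** This is also arguable. The ban gives the DLT assessment period as its reason, and Section 9.2.2.2 uses DLT-equivalent toxicity in Part B.

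**What to change.** In Section 9.2.3, extend the Cycle 1 exception after the mention of a DLT with: *or where a hold or discontinuation is directed by Section 9.2.3.1 or 9.2.3.2*. Citing Section 9.2.3.1 matters because the infusion-reaction rules meet the same literal ban.

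In Section 9.6.1, add one sentence: a patient whose Cycle 1 dose is held for drug-related toxicity without a DLT stays in the safety review and is DLT-evaluable if followed through Day 28, although not counted as having completed the cycle under SAP Section 6.11.1. The event can still be declared dose-limiting under the existing discretionary item.

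The cost is one clause and one sentence at the next amendment, with no change to the DLT definition or the planned sample size. It does touch evaluability, by making explicit what is now unstated. The small downside is that such a patient contributes a DLT assessment on 1 of 2 planned Cycle 1 ramucirumab doses, which the pre-escalation review should take into account.
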